Exploratory Aim 6: Explore the effects of cortisol on resting state functional connectivity using whole brain connectomic mapping.

Exploratory Aim 7: Explore the impact of depressive symptoms on memory and hippocampal structure, activation, connectivity and 1HMRSS outcomes in response to hydrocortisone administration.

2. Background.

- Describe past experimental and/or clinical findings leading to the formulation of your study.
- For research involving investigational drugs, describe the previously conducted animal and human studies.
- For research that involves FDA approved drugs or devices, describe the FDA approved uses of this drug/device in relation to your protocol.
- Attach a copy of the approved labeling as a product package insert or from the Physician's Desk Reference.

You may reference sponsor's full protocol or grant application (section number and/or title) or if none, ensure background includes references.

Please respond to all components of this item, or clearly indicate which components are not applicable.

a. Background

See grant application uploaded in section 4.1.3d of the Smartform. The background information can be found in Section 3 (Research Strategy, pages 68-69).

b. Current practice

N/A

3. Study Design.

Describe the study design (e.g., single/double blind, parallel, crossover, etc.) Consider inserting a scheme to visually present the study design.

The study involves a double-blind, placebo-controlled, crossover design of hydrocortisone in depressed and non-depressed (healthy controls) participants. Within each group (depressed and non-depressed), participants will be randomized to receive

Form A

IRB # STU 2018-0360

hydrocortisone or placebo for 3 days, followed by MRI and cognitive testing on day 3. Participants will then undergo a 25-day washout of study medication and will then, again, receive hydrocortisone or placebo for 3 days, followed by MRI and cognitive testing. The order in which participants will receive hydrocortisone vs. placebo will be randomized by a study statistician.

4. Research Plan / Description of the Research Methods:

4.a. Provide a **comprehensive narrative** describing the **research methods**.

- 1) Provide the **order in which tests/procedures will be performed**,
- 2) Provide the **setting** for these events and a description of the **methods used to protect privacy** during the study.
- 3) Provide the **plan for data analysis** (include as applicable the **sample size calculation**)

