Please respond to all components of this item, or clearly indicate which components are not applicable.

Informed consent and all study procedures, other than neuroimaging, will be conducted at BL8.224 or remotely through secure video conferencing software (e.g. Zoom, Teams). Neuroimaging will be done at the AIRC. When informed consent is conducted remotely, DocuSign will be used to obtain signatures. Please see the next page for the assessment schedule.

Methods used to protect privacy: Deidentified data will be stored in REDCap – a self-managed, secure, web-based solution that is designed to support data collection strategies for research studies. Only researchers associated with the study will have access to any protected health information (PHI). This information will not be stored on REDCap. Identifying information will be kept in a separate password-protected file only accessible to the PI and the research team on a need-to-know basis. Data will be analyzed by group, and subjects will be identified only by a subject ID number to protect their confidentiality. Researchers will destroy the personal identifiers upon completion of data collection for the study.

Data analysis plan:

Aim 1: Determine the effect of cortisol on task-driven hippocampal activation using, for the first time, high-resolution (1.5 mm isotropic) fMRI of hippocampal subfields (i.e., DG/CA3, CA1, subiculum). The design is a two-period crossover with randomized order of treatment conditions, and the primary interest is in the treatment effect on hippocampal subfield activation, estimated as the within-subjects difference in hippocampal subfield activation between the hydrocortisone and placebo treatment conditions. The index of hippocampal subfield activation is a beta-weight of the contrast of the task-active condition vs. the control condition (e.g. novel vs. familiar in the Novelty Detection task and lure correct rejections vs. false alarms in the Mnemonic Discrimination task). We will use linear mixed effects regression to estimate the following model of DG/CA3 activation, Y_{ijk} , of the i^{th} subject in the j^{th} group in the k^{th} period, cast in a traditional longitudinal data setup.

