Electrocardiogram (ECG)	X		X		X
Urine pregnancy test (UPT)	X		X		X
Randomization			X		
Begin 3-day course of hydrocortisone or placebo			X		
Begin 3-day actigraphy monitoring			X		
Structural and functional MRI, spectroscopy			X		X
Follow-up with a clinician			X		X
Adverse events review			X		X
Exit survey			X		X
Approximate time/visit	3 hr	45 m	3.5 hr	45 m	3.5 hr

Form A

IRB #	STU 2018-0360
-------	---------------

4.b. List of the study intervention(s) being tested or evaluated under this protocol

	N/A - this study does not test or evaluate an intervention. Skip to item 4.d.		
#	Study intervention(s) being tested or evaluated under the protocol Add or delete rows as needed	Affiliate Place a check next to institution(s) where the intervention will be performed	Local Standard Practice? Indicate whether the intervention is considered acceptable practice locally for applicable institutions
1	Hydrocortisone	 UTSW	 Yes
		 PHHS	 Yes
		 CMC	 Yes
		 THR	 Yes
		 TSRH	 Yes
		 Other: _____	 Yes

4.c. Risk:Benefit Analysis of study interventions being tested or evaluated under this protocol

For each study intervention identified in section 6b above, complete a risk:benefit analysis table.

(Two tables are provided, copy & paste additional tables as needed or delete both tables if this study does not test an intervention)

Form A

IRB #	STU 2018-0360
-------	---------------

4.c.

Study Intervention #1

Hydrocortisone

List each group exposed to this intervention on a separate line. (e.g., experimental, control, Arm A, Arm B, etc) Or state All Groups/Subjects
	
For each group, list the benefits of this intervention. (Benefits can be directly from the intervention or from a monitoring procedure likely to contribute to the subject's well being). If there are no benefits, state "none".

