
All subjects
	
All subjects will receive ongoing monitoring for their depressive symptoms. However, this is not a treatment study and the researchers are not evaluating the effectiveness of hydrocortisone in treating depression. The researchers are interested in whether a short 3-day dose of hydrocortisone has different effect on the brain and cognition in depressed vs. non-depressed individuals. Participants will also receive blood work, ECG, progesterone level testing, diagnostic interviews, psychiatric symptom assessment, cognitive assessments, and psychiatric care. Thus, we feel that the risks, although clearly present, are greatly outweighed by the benefits of this study.

If you are requesting a Waiver of Informed Consent, complete the table below.

If you have a consent form, list the reasonably foreseeable **risks** in the consent form (and do not complete this section).

List the risks according to the probability (likely, less likely or rare) and magnitude (serious or not serious).

(include: 1) expected adverse events; 2) rare and serious adverse events; 3) all other psychological, social, legal harms)

Do not delete frequency. Frequency must be estimated because it will assist you with determining which adverse events will require prompt reporting.

	Not serious	Serious
Likely These risks are expected to occur in more than 20 out of 100 subjects.	
 • N/A (listed in consent) 	
 • N/A (listed in consent)
Less likely These risks are expected to occur in 5-20 subjects or less out of 100 subjects.	
 • N/A (listed in consent) 	
 • N/A (listed in consent)
Rare These risks are expected to occur in less than 5 subjects out of 100		
 • N/A (listed in consent)

Form A

IRB #	STU 2018-0360
-------	---------------

		
4.d. List ALL other research procedures or components not listed in table 4.b. The combination of Tables 4b and 4d should account for all of the research procedures that will take place during this study.
 
Consider grouping similar procedures under a single component (e.g., blood work, CT = safety assessments)
			

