#	Research component 
 individual procedures 
example: Eligibility Assessments
 
 History and physical Questionnaire Laboratory tests 
Add or delete rows as needed
	Column A Local Standard Practice Indicate the number of times each procedure will be performed as stipulated in the research plan that would be performed if the participant were not participating in the study.	Column B Research Only Indicate the number of times each procedure will be performed solely for research purposes (meaning that the participant would not undergo the same number of procedures or would not undergo the procedure(s) at the same frequency if they were not participating in the study)	Column D Risks If you are requesting a Waiver of Informed Consent, complete the table below. List the reasonably expected risks for each procedure or group of procedures under the following categories as appropriate: 
 • Serious and likely; • Serious and less likely; • Serious and rare; • Not serious and likely; • Not serious and less likely 	
1	Baseline (Visit 1)				N/A – not requesting a waiver of consent
	Informed consent	0	1		
	Psychiatric/medical history	0	1		
	Physical exam	0	1		
	Concomitant medication review	0	1		
	SCID-CV for DSM 5	0	1		
	RAVLT	0	1		
	RULIT	0	1		
	QIDS-C	0	1		
	YMRS	0	1		
	PSS-10	0	1		
	CTQ	0	1		
	C-SSRS	0	1		
	SAFTREE	0	1		
	IPAQ	0	1		
	Blood draw	0	1		
	ECG	0	1		
	Urine pregnancy test	0	1		
	PQ-B	0	1		
	TII	0	1		
2	Visits 2 and 4				
	QIDS-C	0	1		
	YMRS	0	1		
	Clinician follow-up	0	1		
	3-day actigraphy	0	1		
	3-day hydrocortisone vs. placebo	0	1		
3	Visits 3 and 5				
	RAVLT	0	1		
	RULIT	0	1		
	PQ-B	0	1		
	QIDS-C	0	1		
	YMRS	0	1		
	C-SSRS	0	1		
	SAFTREE	0	1		

Form A

IRB #	STU 2018-0360
-------	---------------

Internal Status Scale	0	1	
Blood draw	0	1	
ECG	0	1	
Clinician follow-up	0	1	
MRI (structural and functional)	0	1	
1HMR (spectroscopy)	0	1	
Urine pregnancy test	0	1	
4	Visit 5		
	Exit survey	0	1

Form A

IRB # STU 2018-0360

5. Safety Precautions. (Describe safeguards to address the serious risks listed above.)

a. Describe the procedures for protecting against or minimizing any potential risks for each of the more than minimal risk research procedures listed above.

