The primary risks of this study are potential medication side effects to a brief 3 day exposure to the study medication and a possible delay in treating depression. PI Brown has extensive clinical and research experience with depressed patients, including the studies involving the use of hydrocortisone and neuroimaging. At all visits, the participants will also be assessed by a licensed clinical provider and monitored for side effects, worsening of mood symptoms, and suicidality.

Brief hydrocortisone administration appears to be safe and well tolerated. However, participants will be informed of all potential risks of brief corticosteroid exposure. The participants may experience a brief and reversible change in declarative memory while receiving hydrocortisone.

At the MRI scanner, participants will fill out an MRI screening form and will also be screened by the MRI technologist to ensure it is safe for the participant to undergo the scan. Participants will also be informed that they may stop the imaging session at any time, and participants with claustrophobia will be excluded during the pre-screen. The mock scanner will be available if needed to ensure participants feel comfortable in an enclosed space. Participants will be asked to press the call button in the scanner if they experience any discomfort, and will be immediately removed from the scanner. Both the MRI technologist and the research assistant will be present during the entire MRI session to monitor patient safety. A Rapid Response Team will be called should the patient experience a medical emergency.

All assessments will be performed by trained research personnel experienced in working with the research population involved in the study. Breaks will be utilized as needed to reduce participation burden and psychological stress. Blood will be drawn by a certified phlebotomist. A urine pregnancy test will be administered to all participants of childbearing potential, and pregnant or breastfeeding women will be excluded from the study.

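### Neither 3-day drug course has a urine pregnancy test scheduled at the visit where dosing starts; for course 2 the last scheduled test is about 25 to 26 days old

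*Combined protocol and SAP*

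**What the plan says.** - **Test visits.** In the Assessment Schedule the row "Urine pregnancy test (UPT" is marked at Visits 1, 3 and 5, with nothing at Visits 2 and 4. Table 4.d agrees: the test is in the baseline block and in the block for Visits 3 and 5, and is absent from the block for Visits 2 and 4.
- **Dosing visits.** Table 4.d lists "3-day hydrocortisone vs. placebo" in the block for Visits 2 and 4.
- **Order within a course.** Section 3 gives participants "hydrocortisone or placebo for 3 days, followed by MRI and cognitive testing on day 3". Both tables put imaging ("Structural and functional MRI, spectroscopy" in the Assessment Schedule) at Visits 3 and 5, so those visits close the two courses.
- **Gap between courses.** Section 3: "Participants will then undergo a 25-day washout of study medication".
- **Pregnancy rule.** Section 5.a: "A urine pregnancy test will be administered to all participants of childbearing potential, and pregnant or breastfeeding women will be excluded from the study". It names no visit and does not tie the test to the first dose of either course. The same section asks participants to use effective birth control and has a licensed provider assess them at all visits.
- **Setting.** Section 4.a says that "all study procedures, other than neuroimaging, will be conducted at BL8.224 or remotely through secure video conferencing software", so a dosing visit may take place remotely.

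**The concern.** The plan excludes pregnant women and uses a urine test to check this. A check that guards an exposure belongs immediately before it. Here the tests at Visits 3 and 5 coincide with the scan at the end of each course, and the visits that begin the courses have none. They serve the MRI but not the dosing that precedes it.

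A pregnancy that begins in the washout would therefore meet its first scheduled urine test only after blinded drug had been started. Section 4.c says of this trial that "this is not a treatment study", so a participant has no therapeutic gain to set against an avoidable exposure. What is at stake is participant safety and compliance with the plan's own exclusion. The documents give no figure for the risk of hydrocortisone in pregnancy, so the point rests on the exclusion the plan already makes and not on a quantified harm.

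**Working it through.** **1. Timeline for course 2.** Inputs: 3-day courses with MRI on day 3 and a 25-day washout (section 3); drug at Visits 2 and 4 (table 4.d); MRI and pregnancy test at Visits 3 and 5 (both tables). Take Visit 2 as day 1.

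| Event | Washout counted from Visit 3 | 25 full drug-free days |
|---|---|---|
| Visit 2, course 1 starts | day 1 | day 1 |
| Visit 3, MRI and test | day 3 | day 3 |
| Visit 4, course 2 starts | 3 + 25 = day 28 | days 4 to 28 drug-free, so day 29 |
| Age of last test at first dose | 28 − 3 = 25 days | 29 − 3 = 26 days |
| Visit 5, MRI and test | day 30 | day 31 |

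Visit 5 is day 3 of course 2, so about two days of drug precede its test.

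**2. Timeline for course 1.** The last test before Visit 2 is the Visit 1 test. Its age equals the interval from Visit 1 to Visit 2, which the documents do not state. It could be shorter or longer than 25 days.

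**3. Expected number, course 2.** Assumptions, none of them in the documents: an annual pregnancy rate r of 1% to 10% on birth control, and 40% to 70% women among the 188 enrolled. The 50% in the sample size text for Aims 5 and 7 describes 48 completers, not the enrolled sample. All women are counted as able to conceive.

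Washout pregnancies = women × r × 25/365, where 25/365 = 0.0685.

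| Women | r = 1% | r = 10% |
|---|---|---|
| Per 100 | 0.07 | 0.68 |
| 40% of 188 (75) | 0.05 | 0.52 |
| 50% of 188 (94) | 0.06 | 0.64 |
| 70% of 188 (132) | 0.09 | 0.90 |

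If treatment order is randomised equally, about half of these would be assigned hydrocortisone in course 2. With 94 women that is 0.03 to 0.32. Section 5.a admits women with a hysterectomy or tubal ligation, which lowers every entry.

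**4. What a Visit 4 test could catch.** Suppose a test turns positive L days after conception, with L between 7 and 14 (assumption). Pregnancies missed at Visit 3 and present at Visit 4 began in a window of 25 + L days. A Visit 4 test finds those that began at least L days earlier, a window of 25 days.

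- L = 7: 25/32 = 0.78
- L = 14: 25/39 = 0.64

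This share refers to a longer window than the counts in step 3, so the two should not be multiplied.

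**The case against.** **The Assessment Schedule seems to start drug at Visit 3, where a test is listed.** In the available text its randomization and drug-start rows carry a single mark, under Visit 3. That conflicts with table 4.d, and it cannot be squared with an MRI at Visit 3 on day 3 of dosing. It also marks no start for course 2. The mark may be an artefact of how the table was converted to text. Table 4.d is the coherent source, and no reading of the Visit 3 mark supplies a test at Visit 4.

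**Other safeguards exist.** Birth control is requested. A licensed provider sees participants at all visits, and Visit 4 includes a medication review and a questionnaire. A woman who knows or suspects that she is pregnant could say so before dosing. This stands, and it lowers the risk. None of it is a pregnancy test, and the plan, by testing at three visits, does not itself rely on contraception and self-report alone.

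**The record is incomplete.** The consent form and the grant application are not available here, and either might contain a pre-dose instruction. That cannot be excluded. It would not change the two tables, and the form says that tables 4.b and 4.d together should cover every research procedure.

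**The numbers are small and mostly assumed.** This stands in full. Even the top of the range is below one pregnancy in the trial, with about half of them on placebo in course 2.

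**Conclusion.** The point holds as a scheduling gap in both courses. Neither course has a scheduled urine test at its starting visit. For course 2 the last scheduled test is about 25 to 26 days old at the first dose, reading the visits as table 4.d gives them. For course 1 the age cannot be derived. The expected number of washout pregnancies is about 0.05 to 0.90 over the trial, under assumed pregnancy rates and shares of women. This is a cheap safety improvement, and it does not touch sample size or analysis.

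Three stronger readings are tempting, and the documents do not support them:

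- A reader might infer that no pregnancy test precedes course 2. The tests at Visits 1 and 3 both do; what is missing is one at Visit 4.
- A reader might infer that a washout pregnancy could not come to light before Visit 5. That is true only of scheduled urine tests, since self-report or clinician review could reveal it at Visit 4.
- A reader might infer a material harm to participants. The documents give no risk figure for hydrocortisone in pregnancy, and the expected number is below one.

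**What to change.** Require a negative urine pregnancy test before the first dose of each course, for every participant of childbearing potential. Add the test at Visits 2 and 4 in the Assessment Schedule and in table 4.d, and state the requirement in section 5.a. In the same amendment, correct the drug-start row of the Assessment Schedule to match table 4.d, if the Visit 3 mark is in the source document.

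Keep the tests at Visits 3 and 5. Moving the Visit 5 test to Visit 4 would save a test, but it would remove the check on the day of the MRI and the later look that can pick up conceptions too recent for a Visit 4 test.

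The cost is up to two extra urine tests per woman of childbearing potential, of a kind the trial already uses. If half of the 188 are women, that is at most 94 × 2 = 188 tests, and fewer with dropout before course 2. If the dosing visit is remote, a home test or a brief site visit is also needed.
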